9.9.9. Win Ratio Analyses

Win Ratio analyses, which use hierarchical composite outcomes to compare the RDN and Control groups [14], will be used to analyze the blood pressure and AH medication data at follow-up. A prospective

secondary efficacy analysis will be performed at 6-months using the win ratio approach. The following endpoints will be included in the hierarchical comparison:

1. 24Hr SBP change from SV2 to 6M using a threshold of 5 mmHg
2. Medication burden (INDEX2) change from SV2 to 6M using a threshold of zero

The win ratio statistic is a generalisation of the non-parametric Wilcoxon rank-sum test for comparing continuous outcomes between 2 independent groups to multiple prioritized endpoints. Every RDN subject is paired with every control subject and analysed using the endpoints specified above.

- a) For every pair:
 - i. Calculate the change in the first endpoint (24Hr SBP) from SV2 to 6-months for the RDN subject (Δ_{RDN}) and the control subject (Δ_{CON})
 - ii. Calculate the pairwise treatment effect for the pair: $\Delta_{\text{P}} = \Delta_{\text{RDN}} - \Delta_{\text{CON}}$
 - iii. Compare Δ_{P} to the specified threshold (5 mmHg)
 - iv. if the RDN subject has a better outcome compared to control subject using this threshold ($\Delta_{\text{P}} \leq -5$) then this results in a "win" for the RDN subject. We stop analyzing this pair and move on to the next
 - v. if the control subject has a better outcome compared to the RDN subject ($\Delta_{\text{P}} \geq +5$) then this results in a "loss" for the RDN subject. We stop analyzing this pair and move on to the next
 - vi. if the pairwise treatment effect is smaller than the threshold ($-5 < \Delta_{\text{P}} < +5$) or if either subject has missing data then this pair results in a "tie"
- b) Only pairs classified as ties for the first endpoint (24Hr SBP) proceed to the second hierarchical endpoint of medication burden change and we repeat step a) above using their medication burden change data and a threshold of zero.

After every pair has been analyzed, the win ratio statistic is calculated as the total number of wins divided by the total number of losses from both endpoints. The win ratio will be presented with a 95% confidence interval and p-value.

The ITT population, including the full feasibility cohort, will be used. For medication INDEX2, drug testing data will be used at SV2 and 6-months if available, otherwise the medication burden will be determined using prescribed medication data.

Two additional win ratio sensitivity analyses will be performed using thresholds of 3.5 and 0 mmHg for the 24Hr SBP endpoint and keeping the threshold of zero for the medication burden endpoint. The R package BuyseTest version 2.2.6 will be used to perform these analyses.

9.9.10. % Time in Target Range (TTR%) Analyses

Time in target range (TTR%) analyses [16], which calculate the percentage of time that a subject's BP is within pre-specified BP ranges will be calculated by performing linear interpolation over the days between successive BP measurements, including data from both the baseline and follow-up periods, and summarizing over the entire follow-up time period. Subjects must have a minimum of 2 BP measurements within the TTR time interval to be included in the calculation. All follow-up visits will be included in the TTR analyses. Office SBP TTR will be evaluated using a range of ≤ 140 mmHg and 24Hr SBP TTR will be evaluated using ranges of ≤ 140 & ≤ 130 mmHg. In addition, we will combine Office TTR (≤ 140 mmHg) with 24Hr SBP TTR (≤ 130 mmHg) by taking the maximum value for each subject within the TTR time interval.

For each subject we will calculate their TTR%, using the BP endpoints and BP ranges specified above, in the following time intervals:

- TTR% from baseline to 6-months
- TTR% from baseline to 12-months
- TTR% from baseline to 24-months

- TTR% from baseline to 36-months

These results will be tabulated and compared between treatment arms using non-parametric Kruskal-Wallis tests.

9.10. Safety Evaluation

Adverse Event (AE) information will be collected by the site from subject enrollment (consent) through study termination. AEs will be followed until the event has resolved (in the case of permanent impairment, the event will be followed until it stabilizes, and the overall clinical outcome has been ascertained).

The Investigator will report any adverse events that may occur to the Sponsor, and will assess seriousness, relationship (to the device, procedure and renal denervation therapy where applicable), subsequent intervention required, resolution status and whether or not the adverse event resulted in the subject's discontinuation from the study. The Investigator will provide further information regarding adverse events as requested by the Sponsor.

9.11. Subgroup Analyses

Analysis will be carried out for the following subgroups to assess consistency of results.

- Female vs. male gender
- Age at baseline <65 vs. ≥ 65 years
- BMI by tertiles (kg/m²)
- Type 2 diabetics vs. non-diabetics
- Current smokers vs. former smokers vs non-smokers
- Baseline eGFR <60 vs. ≥60 mL/min/1.73 m²
- Obstructive sleep apnea yes vs. no
- US vs. OUS subjects
- US African American vs. US non-African American subjects
- OUS European vs. Japanese vs. Australian subjects
- Baseline ambulatory SBP by tertiles and medians (mmHg)
- Baseline office SBP by tertiles and medians (mmHg)
- Baseline ambulatory heart rate by tertiles and medians (bpm)
- Baseline office heart rate by tertiles and medians (bpm)
- 24-Hour Pulse Pressure <60 vs. ≥60 mmHg (mmHg)
- Orthostatic hypertension at baseline yes vs. no
- Orthostatic tachycardia at baseline yes vs. no
- Baseline plasma renin activity <0.65 vs. ≥0.65 (ng/mL/h)
- Baseline aldosterone-renin ratio by tertiles
- Baseline aldosterone by tertiles (ng/dL)
- Number of ablations performed by tertiles (RDN arm only)
- Total number of ablations performed in branch vessels by tertiles (RDN arm only)
- Total number of ablations performed in main renal artery vessels by tertiles (RDN arm only)
- Total number of 45 second ablations performed by tertiles (RDN arm only)
- Medication adherent vs. non-adherent subjects at screening visit 2 and 6 months (from urine and serum tests)

- Accessory arteries treated yes vs. no
- 1 vs. 2 vs. 3 prescribed AH medication classes at baseline

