	
 • Section 9.12 added describing analyses related to COVID-19 • As Treated population added in 9.1.3.4 • Added “y_i is the BP change for the ith observation and x_i is the mean centered baseline BP for the ith observation” to section 9.9.4.1. for the definition of the x_i and y_i model parameters • Added “mean centered” to section 9.9.4.1. COMBINE for the definition of the x_i model parameter • Updated Table 3 in section 9.9.4.3 to include 2 decimal places for prior treatment effects • Interim analysis stopping rules in section 9.8 clarified to state that enrollment will stop if stopping rules are met • Primary safety analysis section 9.9.1.1. updated to clarify that primary safety analysis will only be performed once using first 253 subjects • Primary Efficacy Endpoint Analysis section 9.9.4 updated to indicate that the primary analysis treatment effect is Bayesian posterior estimate • Section 9.9.5 updated to include frequentist ANCOVA analyses as secondary analysis of primary efficacy endpoints. Also specifies that secondary cohort subjects will be analyzed using frequentist ANCOVA and will be performed internally • Added attrition rate of 15% to Table 3 in section 9.9.4.3 • Subgroup analyses section updated to include same as OFFMED, to specify complements for every subgroup, and to indicate which subgroups analyses are restricted to the RDN arm • Appendix I (missing data imputation) updated • Appendix VII (section 11.7) added with sensitivity analyses of Bayesian operating characteristics 	

5.1
	
 • First and second interim analysis to take place with 130 and 175 randomized subjects. Sections 8, 9.8, 9.9.4.3, 9.9.5 updated • Bayesian sensitivity analyses added in section 9.9.5 • Appendices describing the algorithms for selecting office BP, 24-hour BP, lab values 	
[name], Senior Principal Statistician

	
and drug testing values removed from SAP, and will only be included in study table specifications
 
 • Validation requirements added in section 10. • SAP template version added to footer 	
5.2	
 • Subgroup analyses for accessory arteries treated and 1 vs. 2 vs. 3 AH Medication Classes at baseline added in section 9.11 	[name], Senior Principal Statistician

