5.1. Primary Endpoints

There are two primary endpoints in this study (one efficacy and one safety). The study will be considered successful if both the primary safety and efficacy endpoint hypotheses are met.

Powered Primary Efficacy Endpoint:

Baseline adjusted change (using analysis of covariance, ANCOVA) in SBP from baseline (screening visit 2, SV2) to 6 months post-procedure as measured by 24-hour ABPM.

Powered Primary Safety Endpoint:

Incidence of Major Adverse Events (MAE), defined as a composite of the following events, through one-month post-randomization (6 months for new renal artery stenosis):

- All-cause mortality
- End-Stage Renal Disease (ESRD)
- Significant embolic event resulting in end-organ damage
- Renal artery perforation requiring intervention
- Renal artery dissection requiring intervention
- Vascular complications
- Hospitalization for hypertensive crisis not related to confirmed non-adherence with medications and/or the protocol
- New renal artery stenosis $> 70\%$, confirmed by angiography and as determined by the angiographic core laboratory

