- Major bleeding according to TIMI definition (i.e. intracranial hemorrhage, $\geq 5\text{g/dl}$ decrease in hemoglobin concentration, a $\geq 15\%$ absolute decrease in hematocrit, or death due to bleeding within 7 days of the procedure)
- Hospitalization for hypertensive crisis not related to confirmed non-adherence with medication and/or protocol

Summary of Health-related Quality of Life (HRQoL) analysis based on reporting measures using accepted QoL instruments (EQ5D)

Additional analyses

The following additional analyses will be conducted:

- Antihypertensive medication usage throughout the study, including escape patients and subjects with medication changes within 6-month follow-up.
- Additional procedural characteristics e.g. treatment duration, frequency of distal renal artery treatment, ablations per vessel, location of ablations, number of ablations per patient and other characteristics will be analyzed to assess their impact on blood pressure.
- Medication adherence will be assessed using results from drug testing. In addition, we will perform analyses to evaluate the effect of medications adherence on BP.
- Analyses looking at long term imaging will be performed.

6. Investigation Plan

The SPYRAL HTN-ON MED study is a multi-center, international, prospective, blinded, randomized, interventional, sham-controlled study. The goal is to demonstrate that catheter-based renal denervation using the Symplicity Spyral catheter and the Symplicity G3 generator is an effective and safe treatment for hypertension when studied in the presence of one, two, or three anti-hypertensive medication classes. Subjects must be on at least 50% of the maximum manufacturer's dosage of antihypertensive medication. Anti-hypertensive medication classes must include a thiazide-type diuretic, a dihydropyridine calcium channel blocker, an ACE-I/ARB, or a beta blocker, (when prescribed with other qualifying medications, 12.5 mg hydrochlorothiazide is acceptable as the minimum dosage).

7. Randomization and Blinding

Randomization will be stratified by study center at a 2:1 (RDN to control) ratio to:

- Denervation group (RDN): Subjects remain blinded and are treated with the renal denervation procedure.
- Control group: Subjects remain blinded and remain on the catheterization lab table for at least 20 minutes prior to introducer sheath removal.

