Investigational sites will access randomization allocation via a password-protected system that can only be accessed by those approved by the study sponsor.

All study staff and necessary hospital personnel will be instructed that subjects are not to be informed of their randomization assignments and appropriate measures should be taken to minimize the risk of premature unblinding.

The Investigator performing the catheterization lab procedures and his/her designated study staff will be blinded to a subject's randomization group up until the angiography is completed and inclusion/exclusion confirmed following the angiography. However, investigators performing study follow-up visits and the subject's referring/managing physicians will not be proactively informed of a subject's treatment assignment to minimize potential bias in the subject's care decisions. To minimize potential bias in the measurement of Office BP and ABPM, each investigational site will specify several designated "blinded" members of their study staff that will not be informed of the subject's group assignments and will be responsible for performing the office blood pressure measurements, conducting ABPM preparation and printing results upon a patient completing the ABPM. Prior to unblinding, the effectiveness of blinding will be assessed by asking blinded study staff which group they believe the subject was randomized to.

Subjects will be blinded during the renal angiogram by a combination of conscious sedation, sensory isolation (e.g., blindfold and music), and lack of familiarity with the procedural details and duration (i.e., subjects will not know the difference between the renal angiography procedure alone and the renal angiography and denervation procedure). Subjects will continue to be blinded by only interacting with blinded site personnel through the 6-month follow-up visit post-procedure. Blinding effectiveness will be assessed by asking the subject which group they believe they were randomized to. All subjects will be unblinded after the completion of their required 6-Month follow-up testing.

8. Determination of Sample Size

This study will be conducted as an adaptive Bayesian trial with an informative prior. A Bayesian power prior approach [3,4] in conjunction with a discount function will be used to incorporate the prior data. The discount function reduces the strength of the prior data if disagreements are observed with the prospective data.

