9.1.3.3. Per Protocol Population

All randomized subjects, meeting the following criteria:

1. Subjects showing medication compliance in blood and/or urine (via drug testing data) at SV2, 3-months, and 6-months, compared with prescribed AH Meds at SV2.
2. Exclude subjects with protocol deviation code 101 (consent not obtained).
3. Exclude subjects who do not meet the following Inclusion/Exclusion criteria:
 - Inclusion: Individual has an office SBP ≥ 150 mmHg and < 180 mmHg and an office DBP ≥ 90 mmHg measured at SV2, according to the guidelines in Appendix L7 of the study protocol.

- Inclusion: Individual has a 24-hour ABPM average SBP ≥ 140 and < 170 mmHg measured at SV2, according to guidelines in Appendix L7 of the study protocol.
 - Exclusion: Individual has undergone prior renal denervation.
 - Exclusion: Individual has renal artery anatomy that is ineligible for treatment.
4. Exclude subjects meeting the anti-hypertensive medication escape criteria (office SBP ≥ 180 mmHg OR < 115 mmHg associated with symptoms of hypotension or safety concern requiring medication changes).
 5. Exclude subjects who did not receive the treatment they were randomized to.

Office and ambulatory blood pressure outcomes out to 6 months follow-up will be presented for this population.

9.1.3.4. Medication Adherence Population 1

All randomized subjects, meeting the following criteria:

1. Subjects showing medication compliance in blood and/or urine (via drug testing data) at SV2, 3-months, and 6-months, compared with prescribed AH Meds at SV2.
2. Exclude subjects meeting the anti-hypertensive medication escape criteria (office SBP ≥ 180 mmHg OR < 115 mmHg associated with symptoms of hypotension or safety concern requiring medication changes).
3. Exclude subjects who did not receive the treatment they were randomized to.

Office and ambulatory blood pressure outcomes out to 6 months follow-up will be presented for this population.

9.1.3.5. Medication Adherence Population 2

All randomized subjects, meeting the following criteria:

1. Subjects showing medication compliance in blood and/or urine (via drug testing data) at 3-months and 6-months, compared with drug testing AH Meds at SV2.
2. Exclude subjects meeting the anti-hypertensive medication escape criteria (office SBP ≥ 180 mmHg OR < 115 mmHg associated with symptoms of hypotension or safety concern requiring medication changes).
3. Exclude subjects who did not receive the treatment they were randomized to.

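### The adherence subgroup in SAP 9.11 uses the 6-month drug test, so that part of it is not a randomized comparison; an SV2-only split would be

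*SAP*

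**What the plan says.** Section 9.11 opens with its purpose: "Analysis will be carried out for the following subgroups to assess consistency of results". One item in the list is "Medication adherent vs. non-adherent subjects at screening visit 2 and 6 months (from urine and serum tests". The ablation-count items carry a restriction, for example "Number of ablations performed by tertiles (RDN arm only"; the adherence item carries none. The section gives no caveat about strata measured after randomization and does not say whether the two visits form one classification or two.

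Section 5.1 fixes the timing. The primary endpoint is the change "in SBP from baseline (screening visit 2, SV2) to 6 months post-procedure as measured by 24-hour ABPM". SV2 is therefore baseline, and 6 months is the outcome visit.

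The same kind of conditioning appears in section 9.1.3.3, where the Per Protocol population requires "Subjects showing medication compliance in blood and/or urine (via drug testing data) at SV2, 3-months, and 6-months, compared with prescribed AH Meds at SV2". Medication Adherence Population 1 (9.1.3.4) repeats that rule. Populations 2 and 3 (9.1.3.5 and 9.1.3.6) use the 3- and 6-month tests against the drugs detected at SV2.

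**The concern.** A subgroup contrast between arms is protected by randomization only if the subgroup variable cannot be affected by treatment. Drug-taking at 6 months can be. A subject whose pressure stays high may begin taking the prescribed drugs, and one whose pressure falls may stop. If that happens to different degrees in the two arms, the adherent RDN subjects and the adherent controls are no longer the same kind of people, and neither are the non-adherent ones.

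The SAP itself treats 6-month drug-taking as something RDN may change. In the win ratio (9.9.9), change in medication burden from SV2 to 6 months is the second hierarchical endpoint, taken from drug testing where available. Section 9.11 uses closely related information as a stratifier.

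At stake is interpretation. In a trial of RDN on top of medication, adherence is one of the first explanations a reader will reach for, whatever the result. A split that mixes in post-randomization behaviour can create or mask an apparent difference between adherent and non-adherent subjects.

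**Working it through.** **Reading the text.** The SAP states no figure to reproduce; the question is when the variable is measured.

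- SV2 test: before randomization. Adherence is independent of arm by design, so a split on it is valid.
- 6-month test: after randomization, at the outcome visit. A split on it is not protected.
- Reading A, one joint class needing both tests: the class is partly defined after randomization.
- Reading B, two separate splits: the SV2 split is sound and only the 6-month split is affected.
- A comparison of RDN with control within strata is inferred from the absence of the RDN-only label. Apart from the accessory-artery line, the other unrestricted subgroups are baseline or fixed features.

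**Illustration of size.** All inputs are assumptions; none is in the SAP. Adherent at SV2: 60% in both arms. Drug effect: 8 mmHg. Non-adherent subjects who start: 20% RDN, 35% control. Adherent subjects who stop: 20% RDN, 10% control. Shifts are RDN minus control, relative to no change in drug-taking; a positive shift makes RDN look less effective.

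Fractions of each arm:

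| | RDN | Control |
|---|---|---|
| Adherent at both visits | 0.6 × 0.8 = 0.48 | 0.6 × 0.9 = 0.54 |
| Stopped | 0.6 × 0.2 = 0.12 | 0.6 × 0.1 = 0.06 |
| Started | 0.4 × 0.2 = 0.08 | 0.4 × 0.35 = 0.14 |
| Adherent at neither | 0.32 | 0.26 |

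*Reading B, the 6-month split:*
- Adherent at 6 months: RDN 0.08 × (−8) / 0.56 = −1.14; control 0.14 × (−8) / 0.68 = −1.65. Shift +0.50 mmHg.
- Non-adherent at 6 months: RDN 0.12 × 8 / 0.44 = +2.18; control 0.06 × 8 / 0.32 = +1.50. Shift +0.68 mmHg.
- Spurious interaction: 0.68 − 0.50 = 0.18, about 0.2 mmHg.

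*Reading A, adherent at both visits versus all others:*
- Adherent at both: no starters or stoppers, so shift 0.
- All others: RDN (0.96 − 0.64) / 0.52 = +0.62; control (0.48 − 1.12) / 0.46 = −1.39. Shift about +2.0 mmHg.
- Spurious interaction: about 2.0 mmHg, or 40% of the 5.0 mmHg difference planned in Table 3.

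**A second mechanism, selection on prognosis.** A simulation of 2,000,000 subjects per setting used 2:1 allocation, SD 12 mmHg (Table 3) and true effects of 0 and −5 mmHg. It assumed a prognostic factor correlated 0.3 to 0.5 with BP change, on which adherence loads 0.3 to 0.6, with worse prognosis meaning lower adherence. Bias in the within-stratum contrast:

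| Adherence at 6 months, control / RDN | Bias (mmHg) |
|---|---|
| 60% / 60% | none beyond simulation error of about 0.05 |
| 60% / 50% | about −0.15 to −0.6 |
| 65% / 45% | about −0.3 to −1.2 |
| 50% / 60% | about +0.15 to +0.6 |

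The bias appears when the true effect is 0 as well as −5, and its sign follows which arm adheres more. With adherence independent of arm, as SV2 adherence is, it vanishes.

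**The case against.** The strongest reply is that the line may simply mean two analyses, one per visit. The valid SV2 subgroup would then already be planned, and the defect would be confined to the 6-month half. That stands. A reader might infer that the whole adherence subgroup has lost randomization; the wording does not support this, because it does not settle which reading is meant.

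A reader might also infer that a bias of known size has been shown. It has not. The starting and stopping rates and the 8 mmHg drug effect are invented. The same inputs shift the unstratified contrast by +0.32 − (−0.64) = +0.96 mmHg, more than either stratum under the two-split reading, so much of that illustration is drug-taking mediating the overall effect. With half of the maximum 221 evaluable subjects in each stratum (an assumption) at 2:1, about 74 and 37, the SE of one stratum contrast is 12 × √(1/74 + 1/37) ≈ 2.4 mmHg and that of the interaction about 3.4 mmHg. An artefact of 0.2 mmHg could not be seen, and even 2.0 mmHg is less than one SE.

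Blinding also helps: "All subjects will be unblinded after the completion of their required 6-Month follow-up testing". It limits changes in drug-taking driven by knowledge of the assignment, but not those driven by the BP response itself.

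Finally, the subgroup has no decision role, and sections 5.2 and 9.9.8 separately plan to study adherence and BP. That lowers the severity. It does not justify leaving a post-randomization split unmarked in a consistency list.

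**Conclusion.** The point holds for the part of the line that uses the 6-month drug test: an RDN–control contrast split on that test is not a randomized comparison, on either reading. A split on SV2 alone would be valid.

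Loss of the protection is certain; actual bias is not. Bias requires 6-month adherence to depend on arm or on the BP response, and it can go either way. Under the stated assumptions the spurious interaction from changed drug-taking is about 0.2 mmHg for separate 6-month strata and about 2.0 mmHg for the joint class. The choice of reading therefore matters more than any other single feature of the line.

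Severity is minor. The primary ITT Bayesian analysis, the success rule and the SAP's operating characteristics do not depend on this subgroup, so it gives no ground for doubting the primary efficacy test.

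**What to change.** In section 9.11:

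1. Define the between-arm adherence subgroup by the SV2 drug test only, and test treatment by SV2 adherence in the ANCOVA. Baseline compliance by drug test is already a planned covariate in section 9.9.5.3, so no new variable is needed.
2. Report 6-month adherence by arm as an outcome.
3. If BP is still compared within 6-month adherence groups, say whether the class is joint or separate by visit, and label the result descriptive and non-randomized.

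In sections 9.1.3.3 to 9.1.3.6, add the same caveat to the Per Protocol population and Medication Adherence Populations 1 to 3. They condition on post-randomization drug tests and feed between-arm comparisons in 9.9.6 and 9.9.7, and for Per Protocol also the secondary Bayesian analysis in 9.9.4.

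The cost is one rewritten line and one caveat. No data are lost, the adherence work under 9.9.8 continues, and no figure in the SAP changes.
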